surrounding the hematoma in patients with ICH. Although many clinical trials have shown the effectiveness and safety of NBO in treating ischemic stroke, there is currently a lack of trials focusing on using NBO to treat ICH.^{3, 5} Accordingly, we conducted a proof-of-concept, single-center, randomized controlled trial to evaluate the safety and efficacy of NBO in treating ICH patients so as to explore an innovative adjuvant therapy for ICH.

6. Objectives

This novel study explores the safety and efficacy of NBO administration for patients with ICH. This trial provides an innovative strategy for facilitating functional independence in patients with ICH.

7. Study Design

7.1 Trial plan

This is a single-center, prospective, assessor-blinded, randomized, controlled, two-arm (1:1 ratio) clinical trial registered at Clinicaltrials.gov (http://www.clinicaltrials.gov; unique identifier: NCT04144868) and has been approved by the Institutional Ethics Committee (Affiliated Hospital of Jiujiang University).

All patients within 24 hours from definite onset time are screened by the cranial computed tomography (CT) to confirm ICH at admission. And then the patients sign the consent and are allocated to two arms: the NBO group and the control group. In the NBO group, patients receive high-flow oxygen via oxygen storage face mask (100% O₂, flow rate 8 L/min, 1 hour, four times daily, and 2 L/min via nasal catheter during intermittent periods, for 7 days) immediately in the emergency room after randomization. In the control group, patients receive 2 L/min flow of 100% O₂ via nasal catheter in the emergency room after randomization, for 24 hours daily for 7 days. Meanwhile, the participants undergo routine medication treatment, including dehydration treatment, antihypertensive therapy and sedative treatment, and if necessary, hematoma aspiration or a decompressive craniectomy will be conducted.

7.2 Eligibility criteria

7.2.1 Inclusion criteria:

 supratentorial hematomas confirmed by admitted cranial CT, with the volume ranging from 10 to 30 mL; (2) age 18-80 years;

(3) National Institute of Health Stroke Scale (NIHSS) ≥ 6 and Glasgow Coma Scale (GCS) > 8 at admission;

- (4) onset-to-enrollment time ≤ 24 h;
- (5) signed informed consent.

7.2.2 Exclusion criteria:

(1) a history of ICH, ischemic attack, brain tumor, brain trauma, and other intracranial injury or disorders;

- (2) pre-stroke modified ranking scales (mRS) \geq 1;
- (3) life-threatening condition;
- (4) pre-stroke complicated with austere diseases such as cancer, heart failure, and respiratory failures;
- (5) severe liver and kidney disorders;
- (6) a history of respiratory diseases;
- (7) poor compliance;
- (8) participation in other clinical trials within the previous three months.

7.2.3 Withdrawal criteria

- (1) Acute respiratory diseases during interventions;
- (2) Acid-base imbalances during interventions;
- (3) Other severe complications that should terminate the interventions immediately;
- (4) Decide to undergo hematoma aspiration or a decompressive craniectomy;

(5) Refuse subsequent treatment and follow-up.

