7.3 Follow-up time point

All included patients are followed-up at baseline, 3 days, 7 days, 14 days and 90 days after randomization, respectively.

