7.4 Randomization and blinding

All patients are enrolled consecutively and randomized in 1:1 ratio to receive 8 L/min flow of 100% O_2 via oxygen storage face mask or 2 L/min flow of 100% O_2 via nasal catheter using a computer-generated randomization code. This is an open label trial, so we adopt a partial blinding strategy where the clinical assessors are blinded to the treatment allocation but the operators are not. That is, the neurological functional scores and imaging tests are assessed by investigators blinded to the

intervention and grouping. The operators responsible for oxygen interventions to the patients are unblinded.

	STUDY PROTOCOL					
	Enrollment	Allocation		Foll	ow-up	
TIMEPOINT	0 day	0 day	3 days	7 days	14 days	90 days
ENROLLMENT						
Eligibility screen	Х					
Informed consent	Х					
Allocation		Х				
INTERVENTIONS						
NBO		←		\longrightarrow		
Control		←		\longrightarrow		
ASSESSMENTS						
Personal data		Х				
Safety evaluation				Х		
NIHSS	Х		Х	Х	Х	
Glasgow Coma Scale	х		Х	Х	Х	
Barthel index						Х
mRS						Х
Cranial CT	Х		Х	Х	Х	
CT perfusion	Х			Х		

8. Trial Flow Chart

NBO, normobaric hyperoxia; CT, computed tomography; NIHSS, National Institute of Health Stroke Scale; mRS, modified Rankin Scale.

9. Interventions

All patients within 24 hours from definite onset time are screened by the cranial CT to confirm ICH at admission. After diagnosis of ICH, the patient or his certigiers will decide whether to participate in this

trial. If they agree, an informed consent will be signed, and allocation will proceed.

Participants will be allocated into two arms:

The NBO group, undergoing high-flow oxygen via oxygen storage face masks (100% O₂, flow rate 8 L/min, 1 hour, four times daily, and 2 L/min via nasal catheter during intermittent periods, for 7 days) immediately in the emergency room after randomization.

The control group, undergoing 2 L/min flow of 100% O₂ via nasal catheter in the emergency room after randomization, for 24 hours daily for 7 days.

Secondary stroke prevention follows the 2022 AHA/ASA guidelines for the diagnosis and treatment of acute intracerebral hemorrhage. All participants are hospitalized for at least 14 days, and if the hematoma expands and causes cerebral hernia, hematoma aspiration or a decompressive craniectomy will be conducted.

10. Measurements

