11.2 Safety outcomes

The 7-day oxygen pressure (PO₂), the 7-day carbon dioxide pressure (PCO₂) and the 7-day PH value, as well as the death rate and the complication rate (including hematoma expansion, pulmonary infections, acid-base imbalances and so forth) during hospitalization.

12. Study Flow Diagram

13. Study Periods

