13.2 In-hospital periods

The patients who are assigned to the NBO group receive 100% O₂ via oxygen storage face masks (flow rate 8 L/min, 1 hour, four times daily, and 2 L/min via nasal catheter during intermittent periods, for 7 days), otherwise, the patients receive 2 L/min flow of 100% O₂ via nasal catheter for 24 hours daily for 7 days. Secondary stroke prevention follows the 2015 AHA/ASA guidelines for the diagnosis and treatment of acute intracerebral hemorrhage.⁶ Blood samples are collected at 7 days. Cranial CT is performed at 3 days, 7 days and 14 days, and cranial CTP is performed at 7 days after randomization. NIHSS score and GCS score are assessed at 7 days and 14 days after randomization.

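### The withdrawal list in 7.2.3 conflicts with follow-up of all patients, and 15.2 has no rule for a missing 90-day mRS

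*Combined protocol and SAP*

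**What the plan says.** Section 7.2.3, placed under the eligibility criteria, gives five withdrawal criteria. The first two are acute respiratory disease and acid-base imbalance arising during the intervention. The others are "Other severe complications that should terminate the interventions immediately", "Decide to undergo hematoma aspiration or a decompressive craniectomy" and "Refuse subsequent treatment and follow-up". Withdrawal is not defined, and the list does not separate stopping study oxygen from leaving the trial.

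Other sections describe operated patients as still in the trial. Section 7.1 names hematoma aspiration and craniectomy among the care that participants receive when needed. Section 9 says "All participants are hospitalized for at least 14 days, and if the hematoma expands and causes cerebral hernia, hematoma aspiration or a decompressive craniectomy" will follow. Section 7.3 says "All included patients are followed-up at baseline, 3 days, 7 days, 14 days and 90 days after randomization".

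The primary outcome (11.1.1) is mRS 0-3 against 4-6 at 90 days, obtained by telephone (13.3); death scores 6 (10.2.1). The full analysis set in 15.2 takes randomised patients whatever treatment they had, provided they have one efficacy evaluation after enrolment. No readable section says how a missing 90-day mRS is handled. The 10% loss in 15.1 is only an allowance in the sample size.

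**The concern.** Four of the five criteria are events after randomisation that may be related to outcome. Under section 9, surgery follows expansion with herniation, so operated survivors are more likely than others to score 4 or 5 at 90 days. Acid-base imbalance and respiratory disease carry no severity threshold and need not mean a poor outcome. They are, however, close to the events that 11.2 counts as safety outcomes, so they could differ in frequency between arms.

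If site staff apply the list in the ordinary sense of withdrawal, a patient can leave the primary comparison in two ways:

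- A patient operated on before the day-3 assessment and then withdrawn may have no evaluation after enrolment and so fall outside the full analysis set.
- A patient with a day-3 NIHSS is in the set but may have no 90-day mRS. With no stated rule, a χ² test or Poisson model would by default leave that patient out.

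If such losses differ between arms, the remaining patients are no longer the groups that were randomised, and the primary comparison is biased.

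**Working it through.** The plan gives no figure on this point to reproduce: there is no withdrawal count, surgery rate or missing-data allowance by reason. What follows is illustration on assumed losses.

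**Inputs.** 48 patients per arm (15.1). Planned good-outcome rates of 81% and 61% (15.1), taken as the nearest whole counts: 39/48 = 81.3% and 29/48 = 60.4%. Planned loss of 10% (15.1): 0.10 × 48 = 4.8, so about 5 in an arm. The split of losses between arms, and the share of lost patients with a poor outcome (q), are assumptions.

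**Formula.** With g good outcomes among 48 and L patients lost, the observed proportion good is [g − L(1 − q)] / (48 − L). The difference is NBO minus control. Losses are written NBO v control.

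**No true effect (29/48 in each arm), every lost patient poor (q = 1):**

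- 5 v 5: 29/43 − 29/43 = 0
- 5 v 1: 29/43 − 29/47 = 0.6744 − 0.6170 = +5.7 points
- 1 v 5: 29/47 − 29/43 = −5.7 points

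**No true effect, 5 v 1, varying q:** [29 − 5(1 − q)]/43 − [29 − (1 − q)]/47

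| Share of lost patients poor | Difference, points |
|---|---|
| 19/48 (40%, same as everyone else) | 0 |
| 60% | +1.9 |
| 80% | +3.8 |
| 100% | +5.7 |

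**Near the planned rates, every lost patient poor.** With no loss the difference is 39/48 − 29/48 = 20.8 points.

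- 5 v 1: 39/43 − 29/47 = 0.9070 − 0.6170 = 29.0 points, a shift of +8.2
- 1 v 5: 39/47 − 29/43 = 0.8298 − 0.6744 = 15.5 points, a shift of −5.3

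**Counting missing mRS as 4-6 (no true effect, 5 v 1).** If all lost patients were poor, the rule restores 29/48 − 29/48 = 0. If they resemble everyone else (q = 19/48), it gives [29 − 5(29/48)]/48 − [29 − 29/48]/48 = 0.541 − 0.592 = −5.0 points. The rule can therefore introduce a bias nearly as large as the one it is meant to remove.

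**The case against.** The strongest reply is that the text already favours the harmless reading. Criteria 1 and 2 are tied to the intervention period, criterion 3 speaks of terminating the intervention, and only criterion 5 names follow-up. Sections 7.1 and 9 keep operated patients as participants, 7.3 makes no exception to day-90 follow-up, and a telephone call does not depend on oxygen having continued. This stands as evidence of what was probably meant. It does not remove the conflict: a decision to operate is still listed as withdrawal beside refusal of follow-up, no section says what happens to withdrawn patients, and analysing patients whatever their treatment does not supply a missing day-90 value.

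Other parts of the reply also stand. Ascertained deaths score mRS 6 without a call, and in-hospital death is collected (11.2), so the exposure is mainly surviving patients. Section 7.1 allows surgery simply when needed, a wider trigger than herniation, and no outcome is given for operated patients. The 5 v 1 pattern puts about a whole arm's planned loss on one side and makes every loss poor and unrecorded, which is an upper-end assumption.

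A reader might infer that unblinded staff could choose who leaves. Section 7.4 says "The operators responsible for oxygen interventions to the patients are unblinded", but nothing shows that these operators decide on surgery or apply 7.2.3, and the clinical assessors are blinded. The text does not say who applies the list.

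**Conclusion.** The point holds as a conflict in the plan with a missing rule, and should be fixed. It is more than an omitted detail: 7.2.3 is a stated rule which, applied in its ordinary sense, removes patients for outcome-related events after randomisation, and 15.2 has nothing to catch them.

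Actual bias is not shown. A reader might infer that operated patients were left out of the primary analysis, or that the result was tilted towards NBO. The documents support neither. They report no withdrawals or operations by arm, and the diagram under "12. Study Flow Diagram" is not readable here, which cannot count against the plan. The direction depends on which arm lost more poor-outcome survivors. With no true effect, the illustrations run from −5.7 to +5.7 points, are zero when losses are equal or lost patients resemble the rest, and reach the ends only for 5 v 1 or 1 v 5 loss with every lost patient poor. If all day-90 calls were made, the bias is zero. Confidence is medium, because the conflict is plain in the text but its consequence is unknown.

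**What to change.** - In 7.2.3, state that criteria 1-4 stop study oxygen only and that only criterion 5 ends follow-up. Clinical decisions do not change.
- Obtain the planned day-90 telephone mRS for every randomised patient who does not refuse contact, and analyse each in the assigned arm. Section 15.1 reports enrolment closed at 96; if follow-up is also over, retrieve day-90 status for any withdrawn patients.
- Report surgery and withdrawals by arm and reason, which would show whether the problem arose at all.
- In 15.2, add one sensitivity analysis for any mRS still missing, for example counting it as 4-6. Keep it as sensitivity only, because that rule can itself bias the comparison.

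The cost is a few sentences in 7.2.3 and 15.2, a few telephone calls, one table and one extra analysis.

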7.3 Follow-up time point

All included patients are followed-up at baseline, 3 days, 7 days, 14 days and 90 days after randomization, respectively.

7.4 Randomization and blinding

All patients are enrolled consecutively and randomized in 1:1 ratio to receive 8 L/min flow of 100% O_2 via oxygen storage face mask or 2 L/min flow of 100% O_2 via nasal catheter using a computer-generated randomization code. This is an open label trial, so we adopt a partial blinding strategy where the clinical assessors are blinded to the treatment allocation but the operators are not. That is, the neurological functional scores and imaging tests are assessed by investigators blinded to the

intervention and grouping. The operators responsible for oxygen interventions to the patients are unblinded.

	STUDY PROTOCOL					
	Enrollment	Allocation		Foll	ow-up	
TIMEPOINT	0 day	0 day	3 days	7 days	14 days	90 days
ENROLLMENT						
Eligibility screen	Х					
Informed consent	Х					
Allocation		Х				
INTERVENTIONS						
NBO		←		\longrightarrow		
Control		←		\longrightarrow		
ASSESSMENTS						
Personal data		Х				
Safety evaluation				Х		
NIHSS	Х		Х	Х	Х	
Glasgow Coma Scale	х		Х	Х	Х	
Barthel index						Х
mRS						Х
Cranial CT	Х		Х	Х	Х	
CT perfusion	Х			Х		

8. Trial Flow Chart

NBO, normobaric hyperoxia; CT, computed tomography; NIHSS, National Institute of Health Stroke Scale; mRS, modified Rankin Scale.

9. Interventions

All patients within 24 hours from definite onset time are screened by the cranial CT to confirm ICH at admission. After diagnosis of ICH, the patient or his certigiers will decide whether to participate in this

trial. If they agree, an informed consent will be signed, and allocation will proceed.

Participants will be allocated into two arms:

The NBO group, undergoing high-flow oxygen via oxygen storage face masks (100% O₂, flow rate 8 L/min, 1 hour, four times daily, and 2 L/min via nasal catheter during intermittent periods, for 7 days) immediately in the emergency room after randomization.

The control group, undergoing 2 L/min flow of 100% O₂ via nasal catheter in the emergency room after randomization, for 24 hours daily for 7 days.

Secondary stroke prevention follows the 2022 AHA/ASA guidelines for the diagnosis and treatment of acute intracerebral hemorrhage. All participants are hospitalized for at least 14 days, and if the hematoma expands and causes cerebral hernia, hematoma aspiration or a decompressive craniectomy will be conducted.

10. Measurements

10.1 Imaging test

10.1.1 Non-contrast cranial CT image

Non-contrast head CT scans are performed to assess the severity of hematoma and perihematomal edema (PHE). A 256-slice CT scanner is used following standard local protocols. Next, 5-mm-thick CT images are measured for hematoma and PHE volumes using the General Electric Company workstation built-in image software. All volume measurements are performed using a semi-automated process involving tracking the perimeter of appropriately high- and low-attenuation areas and calculating the lesion area for each slice multiplied by the slice thickness to obtain the lesion volume. Independent analysis of all images is performed by two doctors blinded to the treatment assignment, and any discrepancies are resolved consensually.

Cranial CT scans are performed at admission, day 3, 7, and 14. Software from United Imaging (United Imaging Healthcare Co., Ltd., Shanghai, China) is used for the automated calculation of hematoma and absolute PHE volumes. The relative PHE is calculated by dividing the absolute PHE volume by the baseline hematoma volume to obtain a dimensionless ratio. The reduction volumes of the hematoma, absolute PHE, and relative PHE follow the defined formula: baseline volume – follow-up volume. Besides, the clearance rate of the hematoma, absolute PHE and relative PHE are calculated as a percentage using the defined formula: $100\% \times (baseline volume - follow-up)$

volume)/baseline volume.

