11.1.2 Secondary outcomes

- (1) mRS distribution at 90 days.
- (2) BI scores at 90 days.
- (3) NIHSS scores at 3, 7 and 14 days.
- (4) GCS scores at 3, 7 and 14 days.
- (5) Hematoma volumes, clearance rate and reduction volume at 3, 7, 14 day.
- (6) Absolute PHE volumes, clearance rate and reduction volume at 3, 7, 14 day.
- (7) Relative PHE volumes, clearance rate and reduction volume at 3, 7, 14 day.
- (8) CBF, CBV, MTT, and TTP at 7 days.

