15.2 Statistical methods

The modified intention-to-treat analysis of efficacy outcomes and safety outcomes were performed on the full analysis set, which was composed of all patients who received randomization independent of treatment and at least 1 efficacy evaluation after enrollment. The χ^2 test was used in the unadjusted analysis. A modified Poisson regression model with robust error estimation was used to analyze the primary outcome and other dichotomous endpoints, with adjustment for prespecified covariates (age, male and onset-to-needle time). Relative risk (RR) with a 95% confidence interval (CI) was calculated in both unadjusted and adjusted analyses. Generalized linear models (GLMs) were used to analyze continuous endpoints, including NIHSS scores, Barthel scale scores, and hematoma and edema volumes. The distribution of mRS was analyzed using an ordinal logistic regression model, and odds ratios (OR) with 95% CI were calculated. Post hoc subgroup analysis was performed for the primary outcome according to age, sex, and baseline NIHSS scores, with an OR of 95% CI. No interim analyses were performed.

A 2-sided P value <.05 is considered statistical significance. Because multiple comparisons potentially cause type I error, findings for secondary outcome analyses should be interpreted as exploratory. SPSS software (version 26, IBM) and R software (version 4.1.0) are used for the statistical analyses.

16. Data Management

The enrolled participants were entered in the case report form (CRF) by the evaluator within 24 hours and entered in the electronic form within 3 days. All of the entered personnel signed on the CRF. The assessors were blinded to allocation information. A data supervisor who was not involved in clinical research is set up for data verification. Two investigators who blinded to allocation information rechecked the original data, and if the data was found to be wrong, the data should be corrected in time. The data of modification and the person who modified it should be recorded to ensure that the data is correct.

17. Data and Security Monitoring Board (DSMB)

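### Hematoma clearance has no rule for operated patients, so either reading of the plan masks expansion in the arm with more operations

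*Combined protocol and SAP*

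**What the plan says.** Section 10.1.1 gives two derived measures. For the first, "The reduction volumes of the hematoma, absolute PHE, and relative PHE follow the defined formula": baseline minus follow-up volume. For the second, "the clearance rate of the hematoma, absolute PHE and relative PHE are calculated as a percentage using the defined formula": the same difference divided by baseline, times 100%. Neither has a term or exception for patients who have had surgery. Section 11.1.2 lists as a secondary outcome "Hematoma volumes, clearance rate and reduction volume at 3, 7, 14 day", and repeats the list for absolute and relative perihematomal edema (PHE). CT is scheduled at admission and on days 3, 7 and 14 (sections 8 and 10.1.1), within a hospital stay of at least 14 days (section 9).

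On surgery, section 9 says that "if the hematoma expands and causes cerebral hernia, hematoma aspiration or a decompressive craniectomy will be conducted". Section 7.1 is broader: "if necessary, hematoma aspiration or a decompressive craniectomy will be conducted". Section 7.2.3 lists as withdrawal criterion 4 "Decide to undergo hematoma aspiration or a decompressive craniectomy", without saying whether withdrawal is from oxygen, from scanning or from the analysis.

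The full analysis set in section 15.2 comprises "all patients who received randomization independent of treatment and at least 1 efficacy evaluation after enrollment". For the model, "Generalized linear models (GLMs) were used to analyze continuous endpoints, including NIHSS scores, Barthel scale scores, and hematoma and edema volumes". Section 15.2 has no rule for surgery or for missing scans. It labels the secondary outcomes exploratory. Section 15.1 names imaging findings together with clinical evaluations as the basis for ending the trial at 96 participants.

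**The concern.** The clearance rate is meant to show how fast the hematoma resolves under oxygen. Aspiration removes blood mechanically, and by section 9 it follows expansion severe enough to cause herniation. A patient whose hematoma grew and was then aspirated can therefore score as a good clearer on the next CT. If that patient is instead withdrawn and not scanned, a failure leaves the volume averages. Neither route shows the expansion in the efficacy result.

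What is at stake is the meaning of an imaging benefit. A lower hematoma volume in one arm could partly reflect more operations in that arm. Operations are not listed as an outcome in sections 11.1 or 11.2, so a reader of the CT results would have no means of telling.

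**Working it through.** **Passages side by side.** Sections 8, 9 and 10.1.1 schedule CT to day 14 and make no exception for operated patients. Section 15.2 retains patients whatever treatment they received. Taken together, these bring a post-operative scan into the endpoint. Section 7.2.3(4) could instead mean that no such scan is taken. The documents do not choose between the two.

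**Inputs.** From the documents: 48 patients per arm (section 15.1), baseline hematoma 10 to 30 mL (section 7.2.1), and the formulas of section 10.1.1. The plan states no figure for clearance, expansions or operations, so there is none to reproduce. All other values below are assumptions. The arm contrast is taken as a simple difference in means.

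**One patient.** Assume 20 mL at baseline, expansion to 40 mL, and 8 mL left after aspiration.
- Post-operative scan: 100 × (20 − 8)/20 = +60%.
- Expanded pre-operative scan: 100 × (20 − 40)/20 = −100%.
- Baseline as the last pre-operative scan: 100 × (20 − 20)/20 = 0%.

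**One arm.** Assume 4 of 48 are operated on and the other 44 average 30%.
- Post-operative scans used: (44 × 30 + 4 × 60)/48 = 32.5%.
- Operated patients missing: 30.0%.
- Baseline carried forward: (44 × 30 + 4 × 0)/48 = 27.5%.
- Expanded volume carried forward: (44 × 30 + 4 × (−100))/48 = 19.2%.

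Using post-operative scans raises the mean by 32.5 − 27.5 = 5.0 to 32.5 − 19.2 = 13.3 points. Leaving the patients out raises it by 30.0 − 27.5 = 2.5 to 30.0 − 19.2 = 10.8 points.

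**Two arms.** Assume 5 operations in one arm and 1 in the other, 20 mL at baseline, expansion to 35 mL (clearance −75%), and medical clearance m of 20% or 40% in both arms. If operated patients score c, the difference (5-operation arm minus 1-operation arm) is (5 − 1)/48 × (c − m) = (c − m)/12.

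| Value used for operated patients | c | m = 20% | m = 40% |
|---|---|---|---|
| Post-operative, 5 mL left | 75% | +4.6 | +2.9 |
| Post-operative, 10 mL left | 50% | +2.5 | +0.8 |
| Post-operative, 15 mL left | 25% | +0.4 | −1.25 |
| Left out | – | 0 | 0 |
| Baseline carried forward | 0% | −1.7 | −3.3 |
| Expanded volume carried forward | −75% | −7.9 | −9.6 |

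With 10 operations against 1, the multiplier is 9/48. The post-operative rows then run from +10.3 to −2.8, and the expanded-volume row gives −17.8 or −21.6.

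In every column, the post-operative and left-out rows lie above both pre-operative rows; that gap is the masking. The post-operative result is an outright advantage only when c exceeds m, that is, when the residual is below 20 × (1 − m): 16 mL at m = 20%, and 12 mL at m = 40%.

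**The case against.** The strongest reply is that this is one unreconciled point about withdrawal. If criterion 4 ends scanning, no surgically removed blood is ever counted. The endpoints are exploratory, the primary 90-day mRS outcome does not use these formulas, and hematoma expansion is reported separately under safety (section 11.2) and as an adverse event (section 14.1). An as-measured analysis also fits the full analysis set. No pre-operative CT is scheduled, so a pre-operative value may simply be the baseline scan, and carrying it to day 14 is a convention.

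Most of this stands, and it limits the weight of the point. It does not remove it: the withdrawal reading exchanges counted blood for informative missingness, and the separate safety count does not correct the volume results. The objection to carry-forward is a reason not to make it the sole main analysis.

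A reader might also infer more than the documents support:
- That every operated patient had an expanding hematoma. Section 7.1 allows surgery on wider grounds than section 9.
- That both readings give the arm with more expansions an advantage. Leaving patients out hides a deficit but creates no gain, and the 15 mL, 40% case reverses the sign.
- That craniectomy removes the hematoma, or that surgery moves PHE in a known direction. Neither is stated.
- That unblinded staff choose who is operated on. Section 7.4 says that those delivering oxygen are unblinded; it does not say who decides on surgery.

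**Conclusion.** The concern holds as a gap in the endpoint definition. As written, the plan either credits aspirated blood as clearance or loses operated patients informatively. Relative to pre-operative volumes, each masks expansion in the arm with more operations. Whether that arm looks better outright depends on the residual volume and on medical clearance.

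The actual size cannot be computed, because the number of operations, the residual volumes and the medical clearance are not given. The 5 to 13 points above illustrate one assumed set of values and do not estimate a bias in this trial. It would be tempting to conclude that the reported imaging benefit was surgical; the documents give no operations by arm, so they neither show nor exclude that. If nobody was operated on, saying so closes the matter.

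The finding bears on exploratory endpoints and leaves the primary outcome untouched. It still merits a change, because section 15.1 rests early stopping partly on imaging.

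**What to change.** - Reconcile sections 7.2.3, 10.1.1 and 15.2: state whether scans after aspiration or craniectomy are taken, and whether they are analysed.
- Report the number operated on in each arm beside every CT volume result.
- Beside the as-measured analysis of hematoma volume, reduction and clearance, present one that uses no post-operative volume. Either take the last available pre-operative CT (the baseline scan, hence 0% clearance, if there is no later one) or rank operated patients as the worst outcome. Choose one and write it down.
- Draw no conclusion of imaging benefit unless the two analyses agree.
- Apply the same sensitivity analysis to absolute and relative PHE, without claiming a direction.

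The cost is SAP wording, one derived-variable rule and a second run of the volume models on existing scans. The drawbacks are that the pre-operative value is a convention and may understate expansion, and that the imaging results may look less favourable. No change to who is operated on is implied.

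### No edema measure is designated as main and no baseline volume is named as a covariate; percentage clearance is left-skewed and can be less efficient than log-scale baseline-adjusted volume

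*Combined protocol and SAP*

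**What the plan says.** Section 10.1.1 (Non-contrast cranial CT image) sets the schedule: "Cranial CT scans are performed at admission, day 3, 7, and 14". The admission scan is the baseline, and section 7.2 allows "onset-to-enrollment time ≤ 24 h". Two derived measures follow. For the first, "The reduction volumes of the hematoma, absolute PHE, and relative PHE follow the defined formula: baseline volume – follow-up volume". For the second, "the clearance rate of the hematoma, absolute PHE and relative PHE are calculated as a percentage using the defined formula": the same difference divided by baseline, times 100%. Relative PHE is obtained by "dividing the absolute PHE volume by the baseline hematoma volume to obtain a dimensionless ratio".

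Section 11.1.2 lists all three forms as secondary outcomes, for example "Absolute PHE volumes, clearance rate and reduction volume at 3, 7, 14 day", with parallel items for hematoma and for relative PHE. None is marked as the principal edema measure.

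Section 15.2 says: "Generalized linear models (GLMs) were used to analyze continuous endpoints, including NIHSS scores, Barthel scale scores, and hematoma and edema volumes". It gives no family, link, scale or covariates for these models. The listed covariates (age, male, onset-to-needle time) appear in the sentence on modified Poisson regression for dichotomous endpoints. The same section calls secondary findings exploratory.

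**The concern.** Three gaps combine.

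- **Baseline adjustment.** Every patient has an admission volume, usually one of the strongest predictors of later volume, yet it is not named as a covariate in the volume models.
- **The form of clearance.** It cannot exceed +100% and has no floor. If edema grows after the admission scan, clearance is negative, and a patient with a small baseline PHE can contribute a value of several hundred percent. It is undefined at a baseline of zero, and no rule covers that case. Section 7.2 bounds baseline hematoma (10 to 30 mL), but nothing bounds baseline PHE.
- **No main measure.** Two PHE outcomes (absolute, relative) × three forms × three visits make 18 comparisons with no order among them.

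At stake are the precision and readability of the edema results in a trial that closed with 48 patients per arm.

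**Working it through.** **No figure of the plan to reproduce.** The documents give no power, SD, correlation or effect for any PHE endpoint. The stated total of 154 concerns 90-day mRS and does not bear on this point.

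**Inputs.** From the documents: the clearance formula (10.1.1), 48 per arm (15.1) and two-sided 0.05 (15.2). Assumed: lognormal volumes with equal log-SD *s* at both scans, correlation ρ of log volumes, and a ratio of 0.75 (25% lower PHE with treatment).

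**Shape of clearance.** The log of follow-up/baseline has SD = *s*√[2(1−ρ)]. With *s* = 0.6, ρ = 0.6 and an assumed 1.8-fold growth, SD = 0.6 × √0.8 = 0.537. In the control arm:
- median = 100(1 − 1.8) = −80%
- mean = 100(1 − 1.8·exp(0.537²/2)) = −108%
- 5th percentile = 100(1 − 1.8·exp(1.645 × 0.537)) = −335%

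The growth factor sets the sign and spread of clearance. It cancels from the power comparison below.

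**Power for clearance, by hand.** Let CV = √[exp(2*s*²(1−ρ)) − 1]. In units of the control mean ratio, the difference is 0.25 and SE = CV × √[(1 + 0.75²)/48] = CV × 0.1804. With *s* = 0.6 and ρ = 0.5: CV = 0.658, SE = 0.1188, z = 2.105, power = Φ(2.105 − 1.96) = 56%.

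**Power for log ANCOVA, by hand.** Difference = −ln 0.75 = 0.2877; SE = *s*√(1−ρ²) × √(2/48). With *s* = 0.6 and ρ = 0.5: SE = 0.1061, z = 2.712, power = Φ(0.752) = 77%.

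**Simulation** (4,000 trials per setting; t-tests for the unadjusted comparisons):

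| *s* | ρ | Clearance | Volume, no baseline covariate | Raw volume, baseline-adjusted | Log volume, baseline-adjusted |
|---|---|---|---|---|---|
| 0.6 | 0.5 | 57% | 57% | 67% | 76% |
| 0.6 | 0.7 | 81% | 57% | 81% | 90% |
| 0.6 | 0.9 | 99.9% | 57% | 99.4% | 100% |
| 0.8 | 0.5 | 32% | 32% | 38% | 52% |
| 0.8 | 0.7 | 53% | 32% | 50% | 69% |
| 0.8 | 0.9 | 97% | 32% | 87% | 98% |

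A separate simulation gave, for clearance against log ANCOVA, 58% v 77% and 83% v 91% at *s* = 0.6 (ρ = 0.5, 0.7), and 34% v 53% and 55% v 68% at *s* = 0.8. The two sets agree to within 2 points.

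**A model that does not favor logs.** With additive normal volumes (CV 0.3, 18% effect), power for clearance / raw adjusted / log adjusted was 71% / 92% / 86% at ρ = 0.5 and 92% / 98% / 94% at ρ = 0.7. All were about 100% at ρ = 0.9.

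**Duplicate outcome.** Let A be absolute PHE and H₀ baseline hematoma volume. Relative-PHE clearance is (A₀/H₀ − Aₜ/H₀)/(A₀/H₀) = (A₀ − Aₜ)/A₀, because H₀ cancels. It equals absolute-PHE clearance for every patient at every visit, so 3 of the 18 comparisons are repeats.

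**The case against.** The plan does not rest on clearance alone. A reader might infer that PHE is analyzed only as a percentage and that baseline serves only as a divisor. The documents do not support that: volume and reduction are also listed, reduction subtracts baseline, and section 15.2 names volumes as model endpoints. Nor does any section specify a t-test on clearance; that comparator is an assumption made here to put a size on the issue.

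A reader might also infer that any baseline-adjusted analysis beats clearance. It does not. In the lognormal settings, raw-scale adjustment only matches clearance at ρ = 0.7 with *s* = 0.6, and falls below it at ρ = 0.7 to 0.9 with *s* = 0.8. The consistent gain is against the log-scale model, which is also the model that fits the simulated data, and that gain nearly vanishes at ρ = 0.9. The documents do not show where this trial lies.

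The small-denominator argument does not carry over to hematoma, whose baseline volume is 10 to 30 mL by eligibility. All these outcomes are exploratory.

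Section 15.1 attributes early termination partly to imaging findings, so one might infer that clearance drove it. The text does not say which imaging measure was used, and section 15.2 denies any interim analysis. That link cannot be drawn.

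These limits stand. They leave untouched the missing covariate, the absence of a main measure, the skew of clearance and the duplicate outcome.

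**Conclusion.** The concern holds as a matter of specification and efficiency. The missing covariate, the missing hierarchy, the lack of a lower bound on clearance and the identity of the two PHE clearance outcomes follow from the text and need no assumption.

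The size of the power loss does rest on assumptions. Against log-scale adjustment, clearance loses about 19 points at ρ = 0.5 (77 − 58 at log-SD 0.6; 53 − 34 at 0.8), 8 to 13 points at ρ = 0.7 (91 − 83; 68 − 55), and almost nothing at 0.9. A volume comparison without the baseline covariate stays at 57% (log-SD 0.6) or 32% (log-SD 0.8) whatever the correlation. The consequence is confined to secondary, exploratory outcomes; the 90-day mRS comparison is not affected.

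**What to change.** - **Main PHE analysis at each visit:** a linear model of log follow-up PHE volume on arm and log baseline PHE volume, reported as a ratio of geometric means with 95% CI. State in advance a small constant to add if zeros occur.
- **PHE clearance:** report as median and IQR by arm, without a P value.
- **Hematoma volume:** adjust the model for baseline hematoma volume. The case for demoting clearance does not extend to hematoma.
- **Relative-PHE clearance:** remove it as a separate outcome, or state that it equals absolute-PHE clearance and report it once.

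The cost is SAP wording and one model per visit on scans already taken. A ratio of volumes is less familiar to clinicians than a percentage. Enrollment has closed, so if the data have already been examined the analysis must be labeled post hoc and shown beside the listed outcomes.
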